#### 6.5.7. Lung Imaging (Chest X-ray/CT/Other) and Final Diagnosis

The number and percent of participants with chest X-ray or chest CT or other diagnostic method performed will be displayed. Among the participants with imaging results, the number and percent of participants with abnormal results will be calculated. This analysis will be performed on the all per-protocol, CAP and RAD+CAP populations. Breakdowns will be provided for final diagnosis of CAP versus not final diagnosis of CAP.

# 6.5.8. Mortality

The number and percentage of participants who died during the study will be summarized along with a 95% confidence interval for the percentage. For participants who died, time to death from study enrolment will be calculated as (Date of death – Visit 1 date + 1). The number and percentage of participants who died within 30 days of study enrolment will also be summarized with a 95%

DMB02-GSOP-RF02 5.0 Statistical Analysis Plan Template 05-Dec-2019
PFIZER CONFIDENTIAL
Page 43
TMF Doc ID: 98.03

CI. We will also summarize the data using the participants who died within 180 days of the study enrolment

Mortality rates will be summarized for CAP, RAD+CAP, Sp+CAP and COVID-19+CAP populations. As per the definition of mortality rate, the numerator will be the number of deaths (within each population, respectively), while the denominator would be the total number of participants with that condition. The method of analysis will be performed as recorded in Section 5.2.1 along with a 95% CI.

# 6.6. Safety Summaries and Analyses

All analyses of safety data will be based on the all enrolled population. Frequencies and percentages for reported AEs, SAEs (overall and Pfizer drug related) and RRIs will be calculated. CIs will not be required. A listing of all AEs reported by the participants will be created showing all the data from the AEs CRF.

#### 7. INTERIM ANALYSES

We will not perform the interim analysis of the primary endpoints, i.e. not evaluting effectiveness of the vaccine. Instead, we will perform descriptive analyses on an *ad hoc* basis throughout the study period, which will include basic characteristics of the study population, overall vaccine coverage among the study population (NOT by the case and control status), disease incidences, and serotype distribution among the study population.

# 9. APPENDICES

# Appendix 1. List of Abbreviations

Abbreviation	Definition
ACIP	Advisory Committee on Immunication Practices
	Advisory Committee on Immunisation Practices
AE	Adverse Event
AIDS	Acquired Immunodeficiency Syndrome
ANOVA	Analysis Of Variance
BMI	Body Mass Index
CAD	Coronary Artery Disease
CAMHB	Cation-Adjusted Mueller-Hinton broth
CAP	Community Acquired Pneumonia
CAPA	Acronym for an epidemiological study assessing the burden of hospitalised community-acquired pneumonia (CAP) due to Streptococcus pneumoniae in adults in Spain using urinary antigen detection (UAD) testing
CAPITA	Community-acquired Pneumonia Immunization Trial in Adults
CDC	United States Centres for Disease Control and Prevention
CI	Confidence Interval
COPD	Chronic Obstructive Pulmonary Disease
COVID-19	Coronavirus Disease 2019
CRB-65	Confusion Urea Respiratory Rate Blood Pressure
CRF	Case Report Form
CT	Computed Tomography
CXR	Chest X-ray
DCT	Data Collection Tool
EC	Ethics Committee
eCRF	Electronic Case Report Form
EUCAST	The European Committee on Antimicrobial Susceptibility Testing
FiO2	Fraction of Inspired
FSFV	First Subject First Visit
HCP	Healthcare Practitioner
HIV	Human Immunodeficiency Virus
ICU	Intensive Care Unit
IEC	Independent Ethic Committee
ID	Identification
IPD	Invasive Pneumococcal Disease
IR.	Incidence Rate

DMB02-GSOP-RF02 5.0 Statistical Analysis Plan Template 05-Dec-2019 PFIZER CONFIDENTIAL Page 46 TMF Doc ID: 98.03

Abbreviation	Definition
IRB	Institutional Review Board
LSLV	Last Subject Last Visit
ISCIII	Instituto de Salud Carlos III
NIP	National Immunisation Program
OR	Odds Ratio
PCR	Polymerase Chain Reaction
PCL	Pfizer Central Laboratory
PCV13	13-valent Pneumococcal Conjugate Vaccine
PCV20	20-valent Pneumococcal Conjugate Vaccine
PI	Principal Investigator
PPV23	23-valent Pneumococcal Polysaccharide Vaccine
PSI	Pneumonia Severity Index
RIP	Regional Immunisation Program
RL	Reference Laboratory
RRI	Research Related Injury
RSV	Respiratory Syncytial Virus
SISPAL	"Sistema de Información en Salud Pública y Alimentación" (in
	Spanish)
SP	Streptococcus pneumoniae, S. pneumoniae
SpO2	Oxygen Saturation Level
SOC	Standard Of Care
TND	Test Negative Design
UAD	Urinary Antigen Detection
US	United States
VE	Vaccine Effectiveness
VT	Vaccine Type

# **Appendix 2. Data Derivation Details**

# Appendix 2.1. Serotypes

Central laboratories will perform pneumococcal serotyping for all participants with *S. pneumoniae* (*Sp*) isolated by culture.

VT is defined as serotypes included in PCV20, PCV13, PCV7 or the PPV23

PCV7 serotypes: 4, 6B, 9V, 14, 18C, 19F and 23F.

DMB02-GSOP-RF02 5.0 Statistical Analysis Plan Template 05-Dec-2019
PFIZER CONFIDENTIAL
Page 47
TMF Doc ID: 98.03

PCV13 serotypes: 1, 3, 4, 5, 6A, 6B, 7F, 9V, 14, 18C, 19A, 19F, and 23F.

PCV20 serotypes: 1, 3, 4, 5, 6A, 6B, 7F, 8, 9V, 10A, 11A, 12F, 14, 15B, 18C, 19A, 19F, 22F, 23F, and 33F.

PPV23 serotypes: 1, 2, 3, 4, 5, 6B, 7F, 8, 9N, 9V, 10A, 11A, 12F, 14, 15B, 17F, 18C, 19F, 19A, 20, 22F, 23F and 33F.

[figure not shown]
NVT are serotypes that are not included in any of PCV20, PCV13, PCV7, or PPV23.

Non-typeable or Untypeable (UT) is defined as a result which could not be serotyped. This is a valid result and so will be summarized as a separate line. Note that this is not the same as a missing serotype result.

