#### Cases and controls for VE against PCV13

The cases are the patients with CAP in whom PCV13 serotypes are identified by any method including UADs, routine culture of blood, pleural fluid, or other high-quality respiratory tract specimen. PCV13 VTs are as follows: 1, 3, 4, 5, 6A, 6B, 7F, 9V, 14, 18C, 19A, 19F and 23F. Only sputum isolates from high-quality specimens (Appendix 4) will be considered in assigning case status. Participants with VT serotype who have also an NVT serotype will also be classified as cases.

The controls are the patients with CAP without a VT serotype (including the CAP events for which the pneumococcus was not identified or pneumococcus was present but the serotype was unknown) that met the inclusion and exclusion criteria. These will serve as test-negative controls. Participants with 6C serotype identified (VT serotype) will be excluded from the controls.

The definition of the immunocompromised persons is given in Appendix 2.4.

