#### Results of Culture and Urine Assays for S. pneumoniae

Sp+ is defined as the identification of Streptococcus pneumoniae via any of the following three diagnostic methods:

Microbiology culture: As part of standard of care, all blood and respiratory specimens (e.g., blood, pleural fluid, transtracheal aspirate, bronchoalveolar lavage or other respiratory tract specimen) will undergo bacterial culture at the local site laboratory for the identification of S. pneumoniae according to their standard methodology. Results of blood cultures (including antibiotic susceptibility) from this standard of care bacterial culture testing will be recorded in the CRF.

DMB02-GSOP-RF02 5.0 Statistical Analysis Plan Template 05-Dec-2019
PFIZER CONFIDENTIAL
Page 21
TMF Doc ID: 98.03

For sputum specimens collected as part of SOC testing, specimen quality will be assessed using the specimen's standard-of-care Gram stain results. Only bacterial culture results from high-quality sputum specimens will be used in case of categorization for the VE analysis. However, all pneumococcal isolates will be serotyped regardless of specimen quality.

Pneumococcal bacterial isolates from standard of care specimens will be shipped and analyzed in the Pneumococcal Reference Laboratory from the Centro Nacional de Microbiología of the Instituto de Salud Carlos III (ISCIII). The following antimicrobials will be evaluated: penicillin, amoxicillin, cefotaxime, erythromycin, clindamycin, tetracycline, and levofloxacin.

- Binax assay: If a positive result is issued from the urine testing, when analysed by the Pfizer VRD laboratory, then it is considered Sp+. This assay does not provide Sp serotype information.
- UAD assay: The UAD-1 detects 13 serotypes (1, 3, 4, 5, 6A, 6B, 7F, 9V, 14, 18C, 19A, 19F, 23F) used in Pfizer's 13vPnC vaccine. The UAD-2 assay, using the same Luminex xMAP bead technology, detects 11 additional serotypes (2, 8, 9N, 10A, 11A, 12F, 15B, 17F, 20, 22F, 33F). A maximum of two serotypes can be reported from each one of the UADs.

Any participant who is not determined as Sp+ by any of the three diagnostic methods will be considered as Sp-, unless they have missing results from all three diagnostic methods. If any culture identified Sp+, antibiotic susceptibility will be assessed at the local laboratory and results are to be entered in the CRF.

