#### Serotype at group level

Vaccine type (VT): If any of the serotypes covered in the 20-valent pneumococcal conjugate vaccine (PCV20), 13-valent pneumococcal conjugate vaccine (PCV13), the 7-valent pneumococcal conjugate vaccine (PCV7) or the 23-valent pneumococcal polysaccharide vaccine (PPV23) are detected either by UAD or culture.

PCV20: If any of the following serotypes 1, 3, 4, 5, 6A, 6B, 7F, 8, 9V, 10A, 11A, 12F, 14, 15B, 18C, 19A, 19F, 22F, 23F, and 33F are detected either by UAD or culture.

PCV13: If any of the following serotypes 1, 3, 4, 5, 6A, 6B, 7F, 9V, 14, 18C, 19A, 19F, and 23F are detected either by UAD or culture

cPCV7 (complimentary seven serotype): If any of the following serotypes 8, 10A, 11A, 12F, 15B, 22F, and 33F are detected by UAD or culture

PCV7: If any of the following serotypes 4, 6B, 9V, 14, 18C, 19F and 23F are detected by UAD or culture

PPV23: if any of the folling serotype 1, 2, 3, 4, 5, 6B, 7F, 8, 9N, 9V, 10A, 11A, 12F, 14, 15B, 17F, 18C, 19F, 19A, 20, 22F, 23F and 33F detected by UAD or culture.

DMB02-GSOP-RF02 5.0 Statistical Analysis Plan Template 05-Dec-2019
PFIZER CONFIDENTIAL
Page 30
TMF Doc ID: 98.03

Non-vaccine type (NVT): If none of the serotypes covered in PCV20, PCV13, PCV7, or PPV23 are detected from both UAD and culture.

Non-typeable (NT): A cultured isolate that could not be serotyped. This is a valid result and so will be summarized as a separate line. Note that this is not the same as a missing serotype result.

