## 6.1.1.2. Primary Endpoint 1- Sensitivity Analyses

Several sensitivity analyses will be performed for estimating the VE against PCV13 VT serotype as well as against PPV23 VT serotype S. pneumoniae.

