In the 3rd sensitivity analysis (Suzuki Method), cases are the hospitalized patients with CAP in whom VT serotypes are identified by any method including UADs, routine culture of blood, pleural fluid, or other high-quality respiratory tract specimen, and the controls are the patients in whom pneumococcus is not detected by any method (culture, UAD, or Binax), similar to a recently published article (Suzuki et al, 2017). The controls will be selected using the propensity score matching as described above. A conditional logistic regression will be employed to estimate odds of exposure to PCV13 among cases versus controls. The VE estimate will be calculated as (1 – odds ratio) × 100%. We will use a two-sided alpha of 0.05 for all analyses.

DMB02-GSOP-RF02 5.0 Statistical Analysis Plan Template 05-Dec-2019
PFIZER CONFIDENTIAL
Page 33
TMF Doc ID: 98.03

In the 4th sensitivity analysis (Broome/Indirect cohort method), cases are the patients with CAP in whom VT serotypes are identified by any method including UADs, routine culture of blood, pleural fluid, or other high-quality respiratory tract specimen, and the controls are the patients having a NVT pneumococcal CAP, i.e. the patients in whom pneumococcus is detected from blood/pleural/high-quality sputum culture, Binax or UAD1/2 positive, and VT serotypes are not identified from culture or UAD1/2. The controls will be selected using the propensity score matching as described above. A conditional logistic regression will be employed to estimate odds of exposure to PCV13 among cases versus controls. The VE estimate will be calculated as (1 – odds ratio) × 100%. We will use a two-sided alpha of 0.05 for all analyses.

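### The SAP defines vaccine type (VT) as 24 serotypes from four vaccines, then uses bare VT to pick cases for PCV13 effectiveness in sensitivity analyses 3 and 4

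*SAP*

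**What the plan says.** **The definition.** Appendix 2.1 states: "VT is defined as serotypes included in PCV20, PCV13, PCV7 or the PPV23". SAP 5.4, under the group-level serotype heading, gives the same union and defines non-vaccine type (NVT) as its complement: "If none of the serotypes covered in PCV20, PCV13, PCV7, or PPV23 are detected from both UAD and culture". Both definitions are general. Neither is limited to a particular table or analysis.

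**Where it is used.** In SAP 6.1.1.2 the 1st and 2nd sensitivity analyses name PCV13 serotypes for their cases. The next two do not.

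- 3rd analysis (controls with no pneumococcus detected): "cases are the hospitalized patients with CAP in whom VT serotypes are identified by any method including UADs".
- 4th analysis (indirect cohort): "cases are the patients with CAP in whom VT serotypes are identified by any method including UADs". Its controls are pneumococcus-positive by culture, "Binax or UAD1/2 positive, and VT serotypes are not identified from culture or UAD1/2".

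Both analyses estimate the odds of exposure to PCV13.

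**What points the other way.** The introduction to 6.1.1.2 speaks of "estimating the VE against PCV13 VT serotype as well as against PPV23 VT serotype", which is vaccine-specific. SAP 3.3.1 lists 13 PCV13 vaccine types, and SAP 6.3.2.1 puts PCV13 in brackets after VT. Protocol 12.1.1 lists the same 13 serotypes for PCV13 cases. It describes the sensitivity analyses as a change of control group, not of case definition.

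**The concern.** A sensitivity analysis should change one thing and leave the estimand alone. If VT takes its formal meaning, the 3rd and 4th analyses also change the outcome, from PCV13-type pneumonia to pneumonia due to any of 24 serotypes. Their estimates would then fall below the primary VE for a reason unrelated to robustness, and a sound primary result could look fragile in two of the four numbered sensitivity analyses.

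The 4th analysis has a second problem. The 11 non-PCV13 serotypes on the UAD-2 panel are the natural source of UAD-positive indirect-cohort controls. Under the union definition they move from the control side to the case side.

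The same bare term appears in the control rule of the main analysis (6.1.1.1) and of the 1st sensitivity analysis. There it conflicts with SAP 3.1, which removes only patients with PCV13 or related serotypes from the controls.

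**Working it through.** **1. Set check.** Inputs are the lists in SAP Appendix 2.1 and the assay panels in SAP 3.4.

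- PCV7 (7 serotypes), PCV13 (13), PCV20 (20) and PPV23 (23) have a union of 24.
- UAD-1 covers the 13 PCV13 serotypes, and UAD-2 "detects 11 additional serotypes (2, 8, 9N, 10A, 11A, 12F, 15B, 17F, 20, 22F, 33F"). 13 + 11 = 24, and the two panels together equal the union.
- Union minus PCV13 = the 11 UAD-2 serotypes. Union minus PPV23 = 6A only, so the mismatch matters far more for PCV13 VE.
- UAD serotypes outside the union: 0 of 24. Under the formal definition no UAD result can qualify an indirect-cohort control. This is set membership, not a patient count: patients positive by culture or Binax with no VT serotype found remain eligible.
- 6C is in none of the four lists, yet SAP 3.3.1 says: "Participants with 6C serotype identified (VT serotype) will be excluded from the controls". That label fits neither meaning of VT.

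**2. The plan's own figure.** SAP 2.2 gives 15% coverage in controls, VE 60%, alpha 0.025 and 80% power, requiring 170 cases and 1,692 controls. With OR = 0.40, case odds of vaccination = 0.40 × 0.15/0.85 = 0.0706, so case coverage = 0.0706/1.0706 = 6.59%. A two-sided two-proportion calculation with continuity correction, 6.59% against 15%, returns 170 and 1,692. The inputs are therefore read as the plan intended.

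**3. Dilution in analyses 3 and 4.** Let f be the share of VT cases with no PCV13 serotype, and assume PCV13 has no effect on those serotypes.

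Case coverage = (1 − f) × 6.59% + f × 15%; VE = 1 − [case odds ÷ (0.15/0.85)].

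| f (assumed) | Case coverage | OR | Apparent VE |
|---|---|---|---|
| 0% | 6.59% | 0.400 | 60.0% |
| 10% | 7.43% | 0.455 | 54.5% |
| 25% | 8.70% | 0.540 | 46.0% |
| 50% | 10.80% | 0.686 | 31.4% |
| 60% | 11.64% | 0.746 | 25.4% |

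At 10% or 20% coverage each VE moves by less than one percentage point.

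**4. A rough anchor for f.** The documents give no serotype split for CAP. Protocol Section 7 gives invasive disease in Madrid adults aged 60 and older for 2013–2015. PCV13 types are 1.25 + 3.45 = 4.70 of 17.09 per 100,000 (27.5%). Serotypes 8 and 22F are put at 25%, with the denominator not stated.

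- If 25% of all disease: 0.25 × 17.09 = 4.27; f = 4.27/(4.27 + 4.70) = 47.6%; VE 32.8%.
- If 25% of non-PCV13 disease: 0.25 × 12.39 = 3.10; f = 3.10/(3.10 + 4.70) = 39.7%; VE 37.5%.

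**5. Main-analysis control rule.** Under SAP 3.1 a serotype 8 patient is a control. Under 6.1.1.1 read with 5.4, that patient is removed. If PCV13 does not affect those serotypes, the expected OR stays 0.40 either way, and only the number of controls changes. With 170 cases and two-sided alpha 0.025:

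| Controls removed (assumed) | Controls | Power | Power, continuity-corrected |
|---|---|---|---|
| 0% | 1,692 | 84.3% | 80.3% |
| 5% | 1,607 | 84.1% | 80.0% |
| 20% | 1,353 | 83.3% | 79.2% |

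**The case against.** The best reply is that nobody would read the 3rd and 4th analyses this way. The introduction to 6.1.1.2 names a PCV13 VT and a PPV23 VT. SAP 3.3.1 and Protocol 12.1.1 list 13 serotypes for PCV13 cases, and the protocol says that only the control group changes. The vaccine may be left unnamed because the same text serves both vaccines. The union definition in 5.4 sits among rules for counting isolates in serotype tables. In the 4th analysis the literal reading contradicts itself, so a programmer would probably stop and ask.

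Much of this stands: a vaccine-specific meaning was very likely intended. It does not settle the matter. The SAP states the union definition twice, once in the data-derivation appendix, and nowhere restricts it. The version history shows Section 5.4 was added in the latest SAP version, while the bare VT in 6.1.1.2 remains unqualified. The switch from PCV13 serotypes in analyses 1 and 2 to VT in 3 and 4 invites a reader to look the term up. The 3rd analysis contains no contradiction that would prompt a query.

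The objection to the magnitude is also partly right. The share f is unknown. The invasive-disease proxy is from an earlier period and another disease presentation, and it uses only two of the 11 serotypes. The calculation is crude and unmatched, whereas these analyses are propensity-matched and conditional. The VE figures show sensitivity to the definition and are not forecasts.

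**Conclusion.** The concern holds. Followed as written, the 3rd and 4th sensitivity analyses estimate PCV13 effectiveness against a mix that includes 11 serotypes PCV13 does not contain, and the 4th cannot use the UAD-positive controls it lists. The controls of the 3rd analysis, who have no pneumococcus detected, are unaffected.

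An expected VE of 60% would read between 54.5% and 25.4% for a non-PCV13 share of 10% to 60%, and about 37% to 33% on the invasive-disease proxy. This rests on 15% coverage in every control group, no PCV13 effect on the other 11 serotypes, and an assumed share.

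Cases in the primary analysis and in sensitivity analyses 1 and 2 name PCV13 serotypes and are not diluted. For the primary result the issue is reproducibility rather than bias: two programmers could build different control groups, at a cost of about one point of power in the range examined. The inconsistency itself is certain. How much VE would shift in practice is not. It should be fixed before the VE analyses are programmed.

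**What to change.** Change the SAP text as follows.

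- **6.1.1.2, 3rd and 4th analyses, cases:** replace VT serotypes with PCV13 serotypes.
- **6.1.1.2, 4th analysis, controls:** pneumococcus detected, with no PCV13 or PCV13-related serotype (for example 6C) identified. This restores the rule in Protocol 12.1.1.
- **6.1.1.1 and the 1st analysis, controls:** replace the reference to VT with no PCV13 or PCV13-related serotype, matching SAP 3.1. The 2nd analysis, which reuses the same matching, then follows.
- **PPV23 VE:** repeat each rule with the PPV23 list.
- **3.3.1:** call 6C a vaccine-related serotype, not a VT serotype.
- **5.4 and Appendix 2.1:** state that the union VT and NVT definitions apply only to the descriptive serotype tables.

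The cost is SAP wording only. No new data are needed, and the protocol does not change because the corrected text matches it.

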## Appendix 2.2. Body Mass Index (BMI) Calculation

Body Mass Index (BMI), also known as Quetelet index, is defined as a ratio of body weight in kilograms (kg) to the square of the body height in meters (m). So the unit of BMI is kg/m^2.: The BMI will be classified as a) Underweight (BMI<18.5), b) Normal (BMI:18.5-24.9), c) Overweight (BMI:25.0-29.9), and d) Obese (BMI≥30.0)

Appendix 2.3. Risk class assignment based on pneumonia severity index

# Appendix 2.4. Risk Classification

#### High risk (immunocompromised)

A participant falls in any of the following medical conditions:

- Asplenia
- Cancer/Malignancy, Hematologic
- Cancer/Malignancy, Solid Tumor
- Chronic Kidney Disease
- Human Immunodeficiency Virus (HIV) AIDS
- Human Immunodeficiency Virus (HIV) No AIDS
- Immunodeficiency
- Immunosuppressant Drug Therapy
- Multiple Myeloma
- Organ Transplantation

#### At-risk (immunocompetent)

A participant does not fall in the high-risk category, but having any one of the following medical conditions:

- Alcoholism
- Asthma
- Celiac Disease
- Chronic Liver Disease with Hepatic Failure
- Chronic Liver Disease without Hepatic Failure
- Chronic Neurologic Diseases
- Chronic Obstructive Pulmonary Disease
- Coagulation factor replacement therapy
- Cochlear Implant
- Congestive Heart Failure

DMB02-GSOP-RF02 5.0 Statistical Analysis Plan Template 05-Dec-2019
PFIZER CONFIDENTIAL
Page 49
TMF Doc ID: 98.03

- Coronary Artery Disease (CAD)
- CSF Leak
- Diabetes Treated with Medication
- Down syndrome
- Living in a nursing home
- Living in a long-term care facility
- Occupational risk with exposure to metal fumes
- Other Chronic Heart Disease
- Other Chronic Lung Disease
- Other pneumococcal disease risk factors
- Previous Invasive Pneumococcal Disease
- Tobacco smoking (Tobacco/E-Cigarettes)

## Low-risk (immunocompetent)

If a participant does not fall in high or at-risk category, then the participant will be classified in the low-risk category. These participants will also be treated as immunocompetent.

Risk factor	Spain's Categorization (Protocol Table 7)	eCRF capture	Characterization for SAP
Age	60 +	DOB and symptom onset date	At risk/ immunocompetent
Alcoholism	immunocompetent	Alcoholism	At risk/ immunocompetent
Chronic heart disease	immunocompetent	Congestive heart or failure or coronary artery disease (cad)/ Other chronic heart disease	At risk/ immunocompetent
Chronic liver disease	immunocompetent	Chronic liver disease without hepatic failure/ Chronic liver disease with hepatic failure	At risk/ immunocompetent

ou:			
Chronic lung disease	immunocompetent	Chronic obstructive pulmonary disease/	At risk/
		Asthma/	immunocompetent
		Other chronic lung disease	
Congenital or acquired	immunocompromised	Asplenia	High-risk/
asplenia			immunocompromised
Cerebrospinal fluid leak	immunocompetent	CSF Leak	At risk/
			immunocompetent
Cochlear implant	immunocompetent	Cochlear implant	At risk/
			immunocompetent
Congenital or acquired immunodeficiencies	immunocompromised	Immunodeficiency	High-risk/
	immunocompotent	Dishates treated with mediantian (not	immunocompromised At risk/
Diabetes mellitus	immunocompetent	Diabetes treated with medication (not include diet controlled)	immunocompetent
Generalize malignancy	immunocompromised	,	High-risk/
Ochcianze manghaney	minunocompromiscu	Cancer/manghancy, some tumor	immunocompromised
HIV infection	immunocompromised	Human immunodeficiency virus (HIV)	High-risk/
		- AIDS/	immunocompromised
		Human immunodeficiency virus (HIV)	
Chronic renal failure	immunocompromised	Chronic kidney disease	High-risk/
Nephrotic syndrome			immunocompromise
Leukemia	immunocompromised	Cancer/malignancy, hematologic	High-risk/
Hodgkin's disease	_		immunocompromise
Lymphoma			đ
Multiple myeloma			
Iatrogenic	immunocompromised	Immunosuppressant drug therapy	High-risk/
immunosuppression			immunocompromised
Antineoplastic	not specified		
chemotherapy			
Solid organ transplant	immunocompromised	Organ transplantation	High-risk/
Bone marrow			immunocompromised
transplantation			
Occupational risk	not specified	Occupational risk with exposure to	At risk/
with exposure to metal fumes		metal fumes	immunocompetent
	not enecified	Chronic nauralogie diseases	At risk/
Neurologic diseases	not specified	Chronic neurologic diseases	immunocompetent
(eg, cerebral palsy and seizures)			minunocompetent
	:	Diii	A4 =:=1=/
Prior IPD	immunocompetent	Previous invasive pneumococcal disease	At risk/
0 1:			immunocompetent
Smoking	immunocompetent	Smoking or e-cigarettes current on	At risk/
		substance abuse CRF	immunocompetent

DMB02-GSOP-RF02 5.0 Statistical Analysis Plan Template 05-Dec-2019 PFIZER CONFIDENTIAL Page 51 TMF Doc ID: 98.03 Items in Madrid column of risk classification grid but not in the Table 7 of the Protocol:

Risk factor	Spain's Categorization	eCRF capture	Characterization in SAP
Down syndrome	not specified	Down Syndrome	At risk/ immunocompetent
Celiac disease	not specified	Celiac disease	At risk/ immunocompetent
Cerebrovascular accident (Stroke)	not specified	Chronic neurologic diseases (specified to include this in CCG)	At risk/ immunocompetent
Coagulation factor replacement therapy	not specified	Coagulation factor replacement therapy	At risk/ immunocompetent
Institutionalized in nursing home or LTC facility	not specified	Nursing home or long-term care facility for those with disability or dependency on subject characteristics/risk determinants eCRF	At risk/ immunocompetent

Items on CRF that are not risk factors in Spain/Madrid:

Risk factor	Spain's Categorization	eCRF capture	Characterization in SAP
Other metabolic disease	Not present	Other metabolic disease	Not a risk factor
Diabetes that is diet controlled	Not present	Diabetes that is diet controlled	Not a risk factor
Pneumonia	Not present	Pneumonia	Not a risk factor

